Abbreviations: BP = blood pressure; C-SSRS = Columbia-suicide severity rating scale; CT = computed tomography; ECG = electrocardiogram; EQ-5D-5L = EuroQol - 5 Dimension - 5 Level; HbA1c = glycated hemoglobin; hsCRP = high-sensitivity C-reactive protein; IWQOL-Lite-CT = Impact of Weight on Quality of Life-Lite-Clinical trials version; MRI = magnetic resonance imaging; MRI-PDFF = magnetic resonance imaging - proton density fat fraction; NAFLD = non-alcoholic fatty liver disease; NASH = nonalcoholic steatohepatitis; OGTT = oral glucose tolerance test; PHQ-9 = Patient Health Questionnaire-9; PR = pulse rate; SF-36v2 = Short-Form 36-item Health Survey Version 2; TNFα = tumor necrosis factor-α; VAS = visual analog scale.

Protocol I8F-JE-GPHZ(b)

Table 3. Study Period III- Early Discontinuation and Follow-Up Period

Activity	Early Discontin	nuation and Follow-U	Comment			
Visit Number	99	ED	801	At ED visit, participants who are unable or unwilling to continue the study treatment for any reason will perform an ED visit. If the participant is discontinuing during an unscheduled visit or a scheduled visit, that visit should be performed as the ED visit. At Visit 801, for participants who discontinue or complete the study within 72 weeks, Visit 801 (safety follow-up visit) should be performed 4 weeks after the last visit during the 72-week treatment period.		
Weeks of treatment	72		4 weeks post end of treatment period			
Allowable duration (days)	±7		±7	The visit date after randomization visit is determined in relation to the date of the randomization visit (± the allowed visit window).		
Fasting visit	X	X	X	If the participant is not fasting, the participant should be called in for a new visit within the visit window.		
Adverse events and product complaints	X	X	X			
Hypoglycemic events	X	X	X			
Concomitant medications	X	X	X			
Lifestyle management counseling		X		Counselling on diet and exercise, to be performed by a dietician or equivalent qualified delegate, will include calculation of individualized energy requirement and methods to change dietary composition and amount of physical activity. The lifestyle management counseling may be delivered on a separate day from the rest of that visit's study procedures but must occur within the visit window.		
Review diet and exercise goals		X				
Participant returns study drugs and injection supplies		X				

Activity	Early Discontin	uation and Follow-U	Comment			
Visit Number	99	ED	801	At ED visit, participants who are unable or unwilling to continue the study treatment for any reason will perform an ED visit. If the participant is discontinuing during an unscheduled visit or a scheduled visit, that visit should be performed as the ED visit. At Visit 801, for participants who discontinue or complete the study within 72 weeks, Visit 801 (safety follow-up visit) should be performed 4 weeks after the last visit during the 72-week treatment period.		
Weeks of treatment	72		4 weeks post end of treatment period			
Allowable duration (days)	±7		±7	The visit date after randomization visit is determined in relation to the date of the randomization visit (± the allowed visit window).		
Fasting visit	X	X	X	If the participant is not fasting, the participant should be called in for a new visit within the visit window.		
Review study participant diary, including study drug compliance		X				
Patient-reported outcome measurer	nents					
SF-36v2, acute form		X				
IWQoL-Lite-CT		X				
EQ-5D-5L		X				
Patient Global Impression of Status		X				
C-SSRS (since last visit version)	X	X	X			
PHQ-9	X	X	X			
Self-harm supplement form	X	X	X			
Self-harm follow-up form	X	X	X			

Activity	Early Discontinuation and Follow-Up Period		Comment	
Visit Number	99	ED	801	At ED visit, participants who are unable or unwilling to continue the study treatment for any reason will perform an ED visit. If the participant is discontinuing during an unscheduled visit or a scheduled visit, that visit should be performed as the ED visit. At Visit 801, for participants who discontinue or complete the study within 72 weeks, Visit 801 (safety follow-up visit) should be performed 4 weeks after the last visit during the 72-week treatment period.
Weeks of treatment	72		4 weeks post end of treatment period	
Allowable duration (days)	±7		±7	The visit date after randomization visit is determined in relation to the date of the randomization visit (± the allowed visit window).
Fasting visit	X	X	X	If the participant is not fasting, the participant should be called in for a new visit within the visit window.
CT and MRI				
Visceral and subcutaneous adipose tissue imaging		X		Image analysis to be conducted centrally. Either CT or MRI can be used for the adipose tissue imaging. The chosen method needs to be consistent between all visits for each participant. At ED visit, CT or MRI should only be performed on participants who have had at least 9 months (36 weeks) study drug exposure; for those participants, the procedures should be done within 2 weeks (+2 weeks) as much as possible of the last dose of study drug.
Hepatic fat fraction by MRI-PDFF (only for participants who enroll as NAFLD)		X		Early discontinuation MRI-PDFF procedures should only be performed on participants who have had at least 9 months (36 weeks) study drug exposure; for those participants, MRI-PDFF procedures should be collected within 2 weeks (+2 weeks) as much as possible of the last dose of study drug.

Activity	Early Discontin	uation and Follow-	Up Period	Comment
Visit Number	99	ED	801	At ED visit, participants who are unable or unwilling to continue the study treatment for any reason will perform an ED visit. If the participant is discontinuing during an unscheduled visit or a scheduled visit, that visit should be performed as the ED visit. At Visit 801, for participants who discontinue or complete the study within 72 weeks, Visit 801 (safety follow-up visit) should be performed 4 weeks after the last visit during the 72-week treatment period.
Weeks of treatment	72		4 weeks post end of treatment period	
Allowable duration (days)	±7		±7	The visit date after randomization visit is determined in relation to the date of the randomization visit (± the allowed visit window).
Fasting visit	X	X	X	If the participant is not fasting, the participant should be called in for a new visit within the visit window.
2-Hour OGTT				
Glucose, insulin, c-peptide		X		Early discontinuation 2-Hour OGTT procedures should only be performed on participants who have had at least 9 months (36 weeks) study drug exposure; for those participants, 2-Hour OGTT procedures should be collected within 2 weeks (+2 weeks) as much as possible of the last dose of study drug and participant must be fasting at least 10 hours prior to start of the OGTT (samples taken at 0, 30, 60, 90, and 120 minutes).
Physical evaluation				
Weight	X	Х	X	At Visit 99, participants wanting to discontinue the study before Week 72 will be asked to return for Visit 99 at 72 weeks ±7 days after randomization primarily for body weight measurement and assessment of adverse events. If the participant is unwilling to attend Visit 99, it should be documented in the participant medical record that the participant has refused to attend.

Activity	Early Discontinuation and Follow-Up Period		Comment	
Visit Number	99	ED	801	At ED visit, participants who are unable or unwilling to continue the study treatment for any reason will perform an ED visit. If the participant is discontinuing during an unscheduled visit or a scheduled visit, that visit should be performed as the ED visit. At Visit 801, for participants who discontinue or complete the study within 72 weeks, Visit 801 (safety follow-up visit) should be performed 4 weeks after the last visit during the 72-week treatment period.
Weeks of treatment	72		4 weeks post end of treatment period	
Allowable duration (days)	±7		±7	The visit date after randomization visit is determined in relation to the date of the randomization visit (± the allowed visit window).
Fasting visit	X	X	X	If the participant is not fasting, the participant should be called in for a new visit within the visit window.
Waist circumference	X	X	X	
Electrocardiogram		X	X	Single ECGs should be collected centrally at ED and Visit 801
Vital signs (sitting BP and PR)		X	X	Vital sign measurements should be taken before collection of blood samples for laboratory testing, at visits where required. The participant should sit quietly for 5 minutes before vital sign measurements are taken. For each parameter, 2 measurements will be taken using the same arm; the recordings should be taken at least 1 minute apart.
Clinical laboratory tests				
Hematology		X	X	
Clinical chemistry		X	X	
Other chemistry				
Cystatin-c		X	X	

Activity	Early Discontinuation and Follow-Up Period		Comment	
Visit Number	99	ED	801	At ED visit, participants who are unable or unwilling to continue the study treatment for any reason will perform an ED visit. If the participant is discontinuing during an unscheduled visit or a scheduled visit, that visit should be performed as the ED visit. At Visit 801, for participants who discontinue or complete the study within 72 weeks, Visit 801 (safety follow-up visit) should be performed 4 weeks after the last visit during the 72-week treatment period.
Weeks of treatment	72		4 weeks post end of treatment period	
Allowable duration (days)	±7		±7	The visit date after randomization visit is determined in relation to the date of the randomization visit (± the allowed visit window).
Fasting visit	X	X	X	If the participant is not fasting, the participant should be called in for a new visit within the visit window.
HbA1c		X	X	
Urine chemistry (albumin, creatinine, albumin/creatinine ratio)		X	X	
Urinalysis		X	X	
Hormones (females)				
Urine pregnancy test		X		A urine pregnancy test will be performed locally for women of childbearing potential
Pancreas (pancreatic amylase, lipase)		X	X	
Endocrine				
Calcitonin		X	X	
Adiponectin (high molecular weight and total) and leptin		X	X	
Insulin and C-peptide		X	X	

Activity	Early Discontinuation and Follow-Up Period		Comment	
Visit Number	99	ED	801	At ED visit, participants who are unable or unwilling to continue the study treatment for any reason will perform an ED visit. If the participant is discontinuing during an unscheduled visit or a scheduled visit, that visit should be performed as the ED visit. At Visit 801, for participants who discontinue or complete the study within 72 weeks, Visit 801 (safety follow-up visit) should be performed 4 weeks after the last visit during the 72-week treatment period.
Weeks of treatment	72		4 weeks post end of treatment period	
Allowable duration (days)	±7		±7	The visit date after randomization visit is determined in relation to the date of the randomization visit (± the allowed visit window).
Fasting visit	X	X	X	If the participant is not fasting, the participant should be called in for a new visit within the visit window.
Lipid panel		X	X	
NAFLD/NASH biomarkers (K-18, Pro-C3, ELF, FIB-4 index)		X	X	
Inflammatory markers (hsCRP and TNFα)		X	X	
Other tests		·		
Immunogenicity		X	X	
Pharmacokinetics		X	X	
Non-pharmacogenetic stored samples		X	X	

Abbreviations: BP = blood pressure; C-SSRS = Columbia-suicide severity rating scale; CT = computed tomography; ED = early discontinuation; EQ-5D-5L = EuroQol - 5 Dimension - 5 Level; HbA1c = glycated hemoglobin; hsCRP = high-sensitivity C-reactive protein; IWQoL-Lite-CT = Impact of Weight on Quality of Life-Lite Clinical trials; MRI = magnetic resonance imaging; MRI-PDFF = magnetic resonance imaging - proton density fat fraction; NAFLD = non-alcoholic fatty liver disease; NASH = nonalcoholic steatohepatitis; OGTT = oral glucose tolerance test; PHQ-9 = Patient Health Questionnaire-9; PR = pulse rate; SF-36v2 = Short-Form 36-item Health Survey Version 2; TNF α = tumor necrosis factor- α .

2. Introduction

In general, the accumulation of slight imbalances in daily energy balance causes weight gain and leads to obesity. Obesity is a major risk factor for many comorbid diseases, such as stroke, coronary artery disease, diabetes, malignant disease, and motor dysfunction, which cause a lower quality of life and shortened life expectancy (JASSO 2016; Haneda et al. 2018). In Japan, body mass index (BMI) ≥25 kg/m² is defined as obese, and an obese person with obesity-related health problems and medically requiring weight loss is defined as having "obesity disease" (Matsuzawa 2011). In particular, 3 metabolic disorders in the obesity-related health disorders (impaired glucose tolerance [IGT], hyperlipidemia, and non-alcoholic fatty liver disease [NAFLD]), are located upstream of the metabolic syndrome (Ito 2003), and promote the onset and progression of complications. The guidelines proposed by the Japan Society for the Study of Obesity (JASSO) also suggest that the objective of medical therapy for obesity disease is to accelerate weight loss safely, leading to improvement in complications of obesity, and to suppress the combined use of multiple drugs in patients who have difficulty achieving weight loss goals by individual efforts alone.

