Self-harm supplement form	X	X	X	At Visit 2, self-harm supplement form can be performed on same day as OGTT test.
Self-harm follow-up form	X	X	X	At Visit 2, self-harm follow up form can be performed on same day as OGTT test.
CT and MRI				
Visceral and subcutaneous adipose tissue imaging		X		Image analysis to be conducted centrally. Either CT or MRI can be used for the adipose tissue imaging. The chosen method needs to be consistent across all visits for each participant.

Activity	Scre	ening	Randomization	Comments
Visit number	1	2	3	
Week of treatment	-4	-2	0	
Allowable deviation (days)	NA	-7/+3	-3/+7	The visit date after randomization visit is determined in relation to the date of the randomization visit (\pm the allowed visit window).
Fasting visit	X	X	X	If the participant is not fasting, the participant should be called in for a new visit within the visit window. Patients must be fasting at least 10 hours before blood sampling.
Hepatic fat fraction by MRI-PDFF (only for participants who enroll as NAFLD)		X		Image analysis to be conducted centrally. For individuals where the MRI-PDFF image quality is in question, and re-capturing and assessment of the MRI image is required before 1 st dose of study drug, due to the turnaround time of a central image analysis, a flexible screening window will be allowed. In such scenarios, a Visit 3 that occurs outside of the visit window will not be considered a protocol deviation.
2-Hour OGTT				
Glucose, insulin, and c-peptide		X		2-Hour OGTT test can occur 0 to 4 days prior to the visit.
Physical evaluation				
Physical examination	X			
Height	X			
Weight	X		X	Body weight must be measured in fasting state.
Waist circumference			X	
Electrocardiogram			X	Triplicate ECGs should be collected centrally at Visit 3.
Vital signs (sitting BP and PR)	X		X	Vital sign measurements should be taken before collection of blood samples for laboratory testing, at visits where required. The participant should sit quietly for 5 minutes before vital sign measurements are taken. For each parameter, 2 measurements will be taken using the same arm; the recordings should be taken at least 1 minute apart.
Clinical laboratory tests				
Hematology	X			
Clinical chemistry panel	X		X	
Other chemistry				

Activity	Scre	ening	Randomization	Comments
Visit number	1	2	3	
Week of treatment	-4	-2	0	

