Allowable deviation (days)	NA	-7/+3	-3/+7	The visit date after randomization visit is determined in relation to the date of the randomization visit (\pm the allowed visit window).
Fasting visit	X	X	X	If the participant is not fasting, the participant should be called in for a new visit within the visit window. Patients must be fasting at least 10 hours before blood sampling.
Cystatin-c	X			
HbA1c	X	X	X	Collection of blood samples for HbA1c can be performed on same day as OGTT test. The collection must be before OGTT test.
Urine chemistry (albumin, creatinine, albumin/creatinine ratio)	X		X	
Urinalysis	X		X	
Hormones (females)				
Serum pregnancy test (β-HCG)	X			A serum pregnancy test will be performed by central laboratory at Visit 1 for women of childbearing potential only.
Urine pregnancy test			X	A urine pregnancy test will be performed locally for women of childbearing potential
Follicle-stimulating hormone test	X			Follicle-stimulating hormone test performed at Visit 1 for postmenopausal women at least 40 years of age with an intact uterus, not on hormone therapy, and who have had spontaneous amenorrhea for more than 1 year without an alternative medical cause.
Screening liver panel	X			Refer to Exclusion Criterion 3. Hepatitis B surface antigen, anti-hepatitis C antibodies and RNA, anti-mitochondrial antibodies should be done as clinically appropriate.
Pancreas (pancreatic amylase, lipase)	X		X	
Endocrine				
Calcitonin	X			
Thyroid stimulating hormone	X			
Adiponectin (high molecular weight and total) and leptin			X	

Activity	Scree	ening	Randomization	Comments
Visit number	1	2	3	
Week of treatment	-4	-2	0	
Allowable deviation (days)	NA	-7/+3	-3/+7	The visit date after randomization visit is determined in relation to the date of the randomization visit (± the allowed visit window).
Fasting visit	X	X	X	If the participant is not fasting, the participant should be called in for a new visit within the visit window. Patients must be fasting at least 10 hours before blood sampling.
Insulin and C-peptide			X	
Lipid panel	X	X	X	Study eligibility was determined by laboratory TG data sampled at Visits 1 and 2, at which fasting blood samples were collected for the assessment of clinical laboratory findings if both TGs are ≥150 mg/dL. Collection of blood samples for lipid panel for Visit 2 can be performed on same day as OGTT test. The collection must be before OGTT test.
NAFLD/NASH biomarkers (K-18, Pro-C3, ELF, FIB-4 index)			X	

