5.3. Lifestyle Considerations

Per the Schedule of Activities (Section 1.3), participants will consult with a dietician, or equivalent qualified delegate, according to local standards, to receive lifestyle management

counseling at Weeks 0, 4, 8, and 12 during dose escalation and then at Week 24, 36, 48, 52, and 60 through 72 weeks as defined in the Schedule of Activities (Section 1.3).

Diet and exercise goals (based on JASSO guidelines) established during the lifestyle management counseling and the importance of adherence to the lifestyle component of the trial will be reinforced at each trial contact by study staff.

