#### 4. Statistical Analyses

#### 4.1. General Considerations

Statistical analysis of this study will be the responsibility of Lilly or its designee. Any change to the data analysis methods described in the protocol will require an amendment ONLY if it changes a principal feature of the protocol. Any other change to the data analysis methods described in the protocol, and the justification for making the change, will be described in the SAP or the clinical study report. Additional exploratory data analyses may be conducted as deemed appropriate.

Unless otherwise noted, all tests of treatment effects will be conducted at a 2-sided alpha level of 0.05, and the confidence interval will be calculated at 95%, 2-sided. In statistical summaries and analyses, data will be analyzed as randomized.

Unless specified otherwise, efficacy and safety will be assessed using the modified intent-to-treat (mITT) population. Baseline is defined as the last non-missing data collected at randomization (prior to first dosing of study drug). Unless specified otherwise, safety assessments will be guided by an estimand comparing safety of tirzepatide doses with placebo irrespective of adherence to study drug. Thus, safety analysis will be conducted using SS.

Summary statistics for continuous measures will include sample size, mean, SD, median, minimum, and maximum. The analysis model to make comparisons among treatment groups relative to continuous measurements assessed over time will be a mixed model for repeated measures (MMRM), with terms of treatment, visit, and treatment by visit interaction, stratification factors, and baseline measurement as a covariate.

Kaplan Meier method will be used for estimation of cumulative event free survival rates over time, and Cox proportional hazards regression analysis will be used to compare hazard rates among treatments.

Summary statistics for categorical measures (including categorized continuous measures) will include sample size, frequency, and percentages. Logistic regression will be used to examine the treatment difference in binary efficacy outcomes if there is a need to adjust for covariates. Otherwise, Fisher's exact test will be used to examine the treatment difference in categorical outcomes.

Summary statistics for discrete count measures will include sample size, mean, SD, median, minimum, and maximum.

For the safety related parameters, the definition of baseline and postbaseline are specified in Table GPHZ.4.1.

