Analysis Dataset	Analysis Type	Baseline	Postbaseline
SS	1.1) Treatment-Emergent Adverse Events	The baseline period is defined as the start of screening and ends prior to the first dose in of study treatment (typically at Week 0).	Starts after the first dose of study treatment and ends at the end of the study period (including off-drug follow up visit).
SS	1.2) Treatment-Emergent Abnormal Labs a , Vital Signs, and ECGs.	Baseline will include all scheduled and unscheduled measurements during the baseline period (Visit 1 to Visit 3)	Postbaseline will be defined as above (1.1). All scheduled and unscheduled measurements will be included.
SS	1.3) Change from Last Baseline to Week xx and to Last Postbaseline for Labs a ,Vital Signs, and ECGs.	The last scheduled and unscheduled non-missing assessment recorded during the baseline period defined above (1.2).	Postbaseline will be defined as above (1.1). Only scheduled visits will be included. The early discontinuation (ED) visits are considered scheduled visits.

Table GPHZ.4.1. Baseline and Postbaseline Definitions for Safety Analysis

Abbreviations: ECGs = electrocardiogram; SS = Safety Analysis Set.

For the primary and secondary efficacy endpoint analyses, data for participants with missing values at the 72-week visit will be imputed based on the method described in Section 4.3.2. Otherwise, missing values will not be explicitly imputed except for the parameters with only 1 postbaseline measure during the analysis period per schedule of activity, where last observation carried forward (LOCF) approach will be applied to impute the endpoint when ED measure is available.

End of study participation for a participant will be the earliest of date of death, date of withdrawal from further participation in the study, or date of safety follow-up visit (Visit 801). For participants considered to be lost-to-follow-up, end of study participation will be the date of lost-to-follow-up reported by the investigator. Participant data included in the database after the last date of study participation (including safety follow-up period) will be excluded from statistical analysis.

Statistical treatment comparisons will only be performed between tirzepatide 10 mg or 15 mg, and placebo. Since the trial is not adequately powered to detect difference among tirzepatide doses, comparisons among tirzepatide doses will not be performed unless otherwise specified.

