## 4.4.2. Main analytical approach

# **4.4.2.1.** Main Analytical Approach for Continuous Measures with Only 1 Postbaseline Measure

For mean change from randomization or actual measurement at 72 week visit, an ANCOVA model will be used.

An ANCOVA model with terms of treatment group, stratification factors: baseline IGT (yes or no); baseline hyperlipidemia (based on TG; yes or no); baseline NAFLD (yes or no) and sex (female, male) as fixed effects, baseline measurement as a covariate.

For measurement with only 1 postbaseline measure during the analysis period per schedule of activity, where LOCF approach will be applied to impute the endpoint when ED measure is available.

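### The efficacy MMRMs use at most one of the two or three scheduled pre-dose readings of lipids, HbA1c, blood pressure, chemistry and UACR as the continuous baseline, giving up some precision on secondary and exploratory endpoints

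*Protocol*

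**What the plan says.** **Schedule (Protocol 1.3, Table 1).** The lipid panel is marked at Visits 1, 2 and 3 (Weeks -4, -2 and 0), with the comment "Study eligibility was determined by laboratory TG data sampled at Visits 1 and 2, at which fasting blood samples were collected". HbA1c is marked at the same three visits; its comment reads "Collection of blood samples for HbA1c can be performed on same day as OGTT test". The rows "Clinical chemistry panel" and "Urine chemistry (albumin, creatinine, albumin/creatinine ratio" are marked at Visits 1 and 3, as is sitting blood pressure. The chemistry panel supplies glucose, ALT, AST, GGT, uric acid and creatinine (Protocol 10.2).

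**Start of intervention.** Study drug is first dispensed at Visit 3. Protocol 5.3 gives "counseling at Weeks 0, 4, 8, and 12 during dose escalation".

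**Efficacy baseline (SAP 4.1; Protocol 9.4.1 is the same in substance).** "Baseline is defined as the last non-missing data collected at randomization (prior to first dosing of study drug". The general MMRM in SAP 4.1 carries one baseline measurement of the analysed variable as covariate.

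**Models.** SAP Tables GPHZ.4.2 and GPHZ.4.4 send lipids, HbA1c, fasting glucose, blood pressure, liver enzymes, uric acid, eGFR and UACR to the MMRM of SAP 4.3.2.1. That section names baseline body weight as the covariate. SAP 4.4.2.1, which has stratification factors "as fixed effects, baseline measurement as a covariate", is the ANCOVA for measures with a single postbaseline value (hepatic fat, VAT/SAT, patient-reported outcomes), so none of these endpoints uses it.

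**The concern.** All the Visit 1 to 3 readings come before randomisation and before study drug, so each carries information about the participant's underlying level. For variables that move from visit to visit, such as triglycerides, blood pressure, ALT and UACR, one reading is a noisy covariate and explains less of the Week 24, 52 and 72 variation than the available readings together. Confidence intervals for the affected endpoints are then wider than the collected data require.

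This matters most where numbers are smallest. The sample size was justified for body weight only, and several lipid and glucose endpoints are further restricted to participants with hyperlipidemia or impaired glucose tolerance at baseline.

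**Working it through.** **1. The plan's own figure.** Protocol 9.2 and SAP 5 claim more than 90% power per dose with 87 per arm, 25% dropout, a difference of 11, SD 10 and two-sided alpha 0.025. With 87 × 0.75 ≈ 65 per arm, the non-central t gives 0.99996. Fisher's exact test at 25% versus 90% gives more than 0.9999. The claim is reproduced. It concerns body weight, for which no gain is claimed here. The documents give no power figure for the endpoints discussed below.

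**2. Formula.** Let rb be the correlation between pre-dose readings, rho the correlation of each with Week 72, and k the number of pre-dose readings used. With equal variances, the residual variance as a share of the outcome variance is

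1 − k·rho² / (1 + (k − 1)·rb).

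For k = 1 this is 1 − rho². When every pre-dose visit has the same rho, entering Visit 3 and the mean of the earlier readings as two covariates gives the same result as using the mean of all k.

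**3. Results.** The documents give neither rb nor rho, so all values are assumptions. k = 2 applies to blood pressure, chemistry and UACR; k = 3 to lipids and HbA1c.

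| rb | rho | residual k=1 | k=2 | k=3 | cut k=2 | cut k=3 |
|---|---|---|---|---|---|---|
| 0.5 | 0.5 | 0.750 | 0.667 | 0.625 | 11.1% | 16.7% |
| 0.7 | 0.7 | 0.510 | 0.424 | 0.388 | 17.0% | 24.0% |
| 0.8 | 0.8 | 0.360 | 0.289 | 0.262 | 19.8% | 27.4% |
| 0.7 | 0.5 | 0.750 | 0.706 | 0.688 | 5.9% | 8.3% |
| 0.9 | 0.7 | 0.510 | 0.484 | 0.475 | 5.1% | 6.9% |
| 0.8 | 0.5 | 0.750 | 0.722 | 0.712 | 3.7% | 5.1% |
| 0.9 | 0.5 | 0.750 | 0.737 | 0.732 | 1.8% | 2.4% |

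As equivalent sample size, a 1.8% cut is 1/(1 − 0.018) ≈ 1.02 times the participants, and a 27.4% cut is 1/(1 − 0.274) ≈ 1.38 times.

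**4. Earlier visits less predictive than Visit 3.** With rb = 0.7, Visit 3 at 0.50 and the earlier visits at 0.45, two separate covariates cut variance by 2.6% (one earlier visit) or 3.7% (two). If the single earlier visit's correlation falls to rb × 0.50 = 0.35, the cut is exactly zero. In large samples it cannot be negative, because the regression chooses the weights. A plain average of all visits can lose: with rb 0.8 between adjacent visits, 0.65 between Visits 1 and 3, and 0.40, 0.45 and 0.50 with Week 72, it is 0.9% worse than Visit 3 alone.

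**5. Triglycerides.** The model already has a hyperlipidemia factor, and eligibility defines hyperlipidemia from Visits 1 and 2 (Protocol 5.1). I simulated log-normal triglycerides (log-SD 0.5, median 120 to 200 mg/dL) with that factor in the model. In all participants the cut falls from 17–27% to about 10–23% when rb = rho (0.5 to 0.8), and is about 2–6% when rb exceeds rho (0.7/0.5, 0.8/0.5, 0.9/0.7, 0.9/0.5).

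**6. Which covariate is being supplemented.** If 4.3.2.1 is applied literally, change from baseline is modelled without the analyte's own baseline. Taking body weight as uninformative for that analyte (an assumption), the residual variance is 2(1 − rho) against 1 − rho² with it. Including the analyte's own Visit 3 value then cuts variance by (1 − rho)/2: 25% at rho 0.5 and 10% at rho 0.8, before any earlier reading is added.

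**The case against.** **Size.** A reader might take 11% (one earlier reading) or 17% (two) as the least that can be gained. The documents do not support that. Those figures need readings about two weeks apart to agree with each other no better than they agree with Week 72, when two of three arms are on drug. Where pre-dose readings agree more closely, the gain drops to about 2%, and to 0.3% at rb 0.95 and rho 0.3. This objection stands. It applies with particular force to any measure that is stable over a few weeks.

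**Inconsistent baseline.** A reader might infer that the SAP contradicts itself, because Table GPHZ.4.1 says "Baseline will include all scheduled and unscheduled measurements during the baseline period (Visit 1 to Visit 3". That row concerns treatment-emergent abnormalities. The next row, for change from baseline, takes the last non-missing value, in line with the efficacy rule.

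**Earlier data not wholly discarded.** Step 5 shows that a hyperlipidemia factor built from Visits 1 and 2 absorbs part of the triglyceride gain. This stands if the factor is built that way. SAP 4.4.1.2 instead defines hyperlipidemia by measured triglycerides at baseline, which under SAP 4.1 means Visit 3. For blood pressure, two readings are taken per visit and SAP 4.5.3.4 averages them, so the Visit 3 value is already less noisy than a single reading.

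**Screening diet.** Protocol 5.3.1 speaks of the recommended diet continuing after randomisation, so some change during screening cannot be ruled out. That could lower the gain. It cannot bias the comparison, because the readings precede randomisation.

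**Importance.** A last-value baseline is valid and pre-specified, and the endpoints concerned lie outside the multiplicity-controlled tests. This stands and sets the severity.

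**Conclusion.** The visit counts, the single-value baseline and the absence of the earlier continuous readings from every efficacy model are all confirmed. The consequence is some lost precision on secondary and exploratory endpoints. Under the assumed correlations the residual-variance reduction available is roughly 2% to 27%. It is highest for noisy measures, near the low end where pre-dose readings agree closely relative to Week 72, and smaller for triglycerides to the extent that the hyperlipidemia factor reflects Visits 1 and 2. The range rests on assumed correlations, equal variances and a simple correlation pattern. Blinded screening data would narrow it.

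Two stronger inferences fail. The plan is not biased or invalid on this point, and the co-primary analysis is not weakened, since its power is already near 100%. Nor do the documents establish that the analyte's own baseline is left out of the models: SAP 4.1 includes it and 4.3.2.1 names body weight, so the text is unresolved. This is a free improvement of low severity.

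**What to change.** In SAP 4.1 and 4.3.2.1, for lipids, HbA1c, fasting glucose, systolic and diastolic pressure, ALT, AST, GGT, uric acid, eGFR and UACR:

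- State that the analyte's own Visit 3 value is the baseline covariate, which resolves the conflict with body weight in 4.3.2.1.
- Keep Visit 3 as the reference for change, for the baseline subsets and for responder rules such as the 30% triglyceride reduction. Averaging Visits 1 to 3 into a new baseline would bring regression to the mean into a variable selected at 150 mg/dL or more.
- Add the mean of the earlier scheduled pre-dose values (Visit 1, and Visit 2 where collected), on the analysis scale, as a second covariate. Use the Visit 3 value if the earlier ones are missing.

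SAP 4.4.2.1 needs no change for this. The cost is a sentence or two in the SAP and one more covariate per model, with no new data and no change to any endpoint. It should be settled before unblinding.
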